4.6 VARIABLES

The outcomes of interest are severe complications of diarrhoea including dehydration that requires intravenous rehydration, dehydration that requires oral rehydration with solutions of electrolytes, electrolyte imbalance (potassium and sodium), oliguria, anuria, new onset-thromboembolism, new-onset orthostatic hypotension, new-onset syncope, new-onset dizziness, new-onset vertigo, acute renal failure, hypovolemic shock, hospitalisation due to diarrhoea, stupor, coma, or death.

All variables will be identified using diagnostic and procedure codes from general practitioner (GP) electronic medical records. IBS type and safety outcomes will be validated through a questionnaire to physicians treating the cases and controls included in the study.

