- For Spain, the Information System for the Development of Research in Primary Care (SIDIAP) is a primary care database that collects longitudinal data from electronic medical records (EMRs) from 274 primary care centres in Catalonia since 2006, representing approximately 12% of the Spanish population. Data from primary care, specialised care, hospitals, and pharmacies are available, as well as patient characteristics like gender and date of birth, GP-diagnosed conditions, GP prescriptions, prescription dosing and size, date of prescription and dispensation, laboratory test results, other procedures, specialist referrals and diagnosis, hospital referrals, hospital procedures and discharge diagnosis, death date, and pregnancy information. GP diagnoses are coded following the ICD-10 codes, and hospital admissions are classified following the International Statistical Classification of Diseases and Related Health Problems, Ninth Revision (ICD-9). Since 2018, SIDIAP no longer allows the possibility to contact physicians for extracting extended additional information on the patient through long questionnaires. However, there is the possibility of a text review of the primary care records. This text review can be used to validate cases of interest and it would be conducted by IDIAP's clinical researchers. For this study, it is recommended by the data custodians that a review of free-text in the patient's medical records is conducted to improve the validity of the actual study, in place of the previously planned validation strategy using questionnaires to GPs. This free-text review will be made after an anonymisation process of the clinical records and a natural language processing of the text.
- For Sweden, the National Patient Registry (NPR) and Prescribed Drug Register (PDR): Information on diagnoses will be obtained from the Swedish NPR, which covers all public inpatient care since 1987 and all outpatient visits since 2001. The medical data include main and up to 21 secondary diagnoses and up to 30 surgical procedures from public and private service providers (National Board of Health and Welfare (Sweden), 2012). Diagnoses are coded using ICD-10 codes and surgical procedures with the Nordic Classification of Surgical Procedures. Primary care is not yet covered in the NPR. At present, the NPR is updated once a year.

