8.2 OPERATIONAL OBJECTIVES

- To estimate the risk (case-control OR) of SCD (case) among patients with IBS-C (source population) who received linaclotide prescription vs those who did not, controlling for other potential SCD risk factors (socio-demographics, comorbidities [up to 15], co-medications [up to 15] and other potential variables of interest [up to 10])
- To describe the crude incidence of diarrhoea among patients with IBS-C (source population)

If allowed by the results of the cases and controls validation as discussed below:

- To describe the crude incidence of SCD among patients with IBS-C (source population) prescribed linaclotide (first-time users)
- To describe the crude incidence of SCD among patients with IBS-C (source population) prescribed linaclotide (first-time users) who are at increased risk of SCD:
 - o Patients ≥ 65 years
 - o Patients with hypertension, diabetes, or cardiovascular disease diagnostic codes

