Inclusion/exclusion criteria for Spain and Sweden will be the same but adapted to the respective database specifics.

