9.2.1.2 CASE DEFINITION

Among patients with IBS-C, SCD cases will be patients suffering from diarrhoea (as documented by diagnostic codes) and subsequently (between the diarrhoea diagnosis date and 45 days afterwards) any of the following outcomes:

- Dehydration that requires intravenous rehydration
- Dehydration that requires oral rehydration with solutions of electrolytes
- Electrolyte imbalance: potassium (serum potassium levels 3.0–3.5 mEq/L or < 3.0 mEq/L) and sodium (serum sodium levels > 150 mEq/L)
- Oliguria (urine output < 400 mL in 24 h)
- Anuria (urine output < 50 mL in 24 h)

-
- New-onset thromboembolism episodes
 - New-onset orthostatic hypotension
 - New-onset syncope
 - New-onset dizziness
 - New-onset vertigo
 - Acute renal failure
 - Hypovolemic shock
 - Hospitalisation due to diarrhoea
 - Stupor
 - Coma
 - Death (death certificates will be requested to confirm the cause of death)

The case index date is the date of the first diarrhoea episode that is followed by the first recording of any of the previous outcomes from the list above.

Results of laboratory tests will be available as recorded into only two of the proposed data sources: in CPRD they are manually recorded, especially when they are abnormal; they are automatically recorded in the SIDIAP but there is no lab data information from the Swedish NPR.

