9.5 STUDY SIZE

If we assume a combined population in the UK, Sweden, and Spain of approximately 120 million people (Eurostat, 2014), a prevalence of IBS recorded in primary care of 3.5% (Harkness et al., 2013) and roughly one-third of those corresponding to IBS-C (Tillisch et al., 2005), then the three proposed databases could be expected to include around 216,000 active IBS-C patients. By December 2016, it was estimated that approximately 9,665 patients would have been exposed to linaclotide in the three target databases, for a combined exposure of more than 4,572 patient-years, with the UK contributing approximately 28% of patients, Spain 25%, and Sweden 47%. These estimated number of patients exposed to linalcotide is now expected to be reached by end of December 2017, so the data collection period has been extended accordingly.

Linaclotide clinical trial results (12 and 26 weeks in length) suggest that about 3% of IBS-C patients exposed to placebo and 19.6% of IBS-C patients exposed to linaclotide will experience diarrhoea over those periods, predominantly within the first weeks of initiating therapy. Among them, 4% in the placebo group and 10.1% in the linaclotide-exposed group will experience severe diarrhoea. Therefore, severe diarrhoea was experienced by 0.13% of all IBS-C patients exposed to placebo and by 1.99% of IBS-C patients exposed to linaclotide (Chey et al., 2012; Rao et al., 2012). Other treatments for patients with IBS-C are also associated with diarrhoea, usually of mild severity (Wood, 2012). Information sent to healthcare professionals by the manufacturer of a drug sometimes prescribed for IBS-C patients in the United States (US) warned of very serious diarrhoea complicated with hypovolaemia, hypotension, and syncope that required admission to the hospital and intravenous therapy in approximately one in 2,500 patients (or 0.04%) (Wooltorton, 2004).

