9.7 DATA ANALYSIS

Country-specific analyses will be conducted, and the heterogeneity of the results will be tested. If heterogeneity is not confirmed, then a pooled analysis will be conducted, and country effect will not be assessed.

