The CPRD provides a large, diverse, and representative sample of UK people using primary care services, which allows for generalizability of the study findings to the broader UK population. The General Practice Research Database (GPRD), predecessor to CPRD, has been widely used for observational studies, with over 890 studies published to date in peer-reviewed journals. The SIDIAP database includes information for 90% of the population in Catalonia, a region in northeast Spain, and resembling the data collected by the UK databases. One limitation is that date of prescription is only available for the first prescription and, thereafter, only an approximate date of dispensation is available. For Sweden, the NPR and PDR cover the entire Swedish population and have been previously used in observational studies including drug utilisation ones. However, no primary care data will be available, so diagnoses will be those determined by a specialist, which are expected to be required for the variables of interest for this study. The PDR is not complete with regard to drugs used in nursing homes.

According to the National Board of Health and Welfare, about 1% of people aged 65–79 years live in nursing homes, and about 20% of people aged 80 or more years live in nursing homes in Sweden [Socialstyrelsen]. This may be reflected in potential lower numbers of elderly patient using linacotide identified in Sweden.

The validity of research findings based on CPRD data and data from the other databases depends on the quality and completeness of the data recorded. We are only able to identify comorbidities for which the patient has consulted their GP. Referrals are not always uniformly coded and may appear as free-hand text or letters within the database.

Interval censoring might have an impact on the precision of the results.

Additionally, the proposed linked data sources (i.e., HES OP, HES AE and HES APC) have different linkage coverage periods. In particular, HES OP and HES AE linkage periods are considerably shorter than that of HES APC. This might increase the risk of SCD cases being underestimated. Finally, potential SCD are not classified by severity.

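### Swedish diarrhoea and SCD are hospital/specialist-recorded events, yet the plan gives them the same definition as UK and Spanish events and allows all three countries to be pooled

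*Protocol*

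**What the plan says.** - **Swedish data.** Section 4.7: "Primary care is not yet covered in the NPR". Section 9.9 repeats the gap but treats it as harmless for the study's variables: "no primary care data will be available, so diagnoses will be those determined by a specialist, which are expected to be required". Section 9.2.1.2 notes that this register has no laboratory results, and Section 9.2.1.4 says that Sweden has no validation study.
- **Case definition.** Section 9.2.1.2: "SCD cases will be patients suffering from diarrhoea (as documented by diagnostic codes) and subsequently (between the diarrhoea diagnosis date and 45 days afterwards". A list of qualifying outcomes follows. The list runs from coma and death to new-onset dizziness, new-onset vertigo and dehydration needing oral electrolyte solutions. Section 9.3.2 repeats it and draws on primary-care laboratory results. No Swedish version is given. The only adaptation mentioned concerns cohort entry (9.2.1.1): "Inclusion/exclusion criteria for Spain and Sweden will be the same but adapted to the respective database specifics".
- **Source of variables.** Section 4.6 of the abstract: "All variables will be identified using diagnostic and procedure codes from general practitioner (GP) electronic medical records".
- **Objectives.** Section 8.2 lists crude incidence of diarrhoea in the IBS-C source population, outside the group of objectives that depend on validation. Crude incidence of SCD in linaclotide users is inside that group.
- **Pooling.** Section 9.7 plans country-specific analyses and a heterogeneity test. Then: "If heterogeneity is not confirmed, then a pooled analysis will be conducted". Sections 4.9 and 9.7 add that country effect will then not be assessed.

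**The concern.** An SCD case cannot exist without a coded diarrhoea diagnosis. In Sweden an episode seen only in primary care leaves no such code, so it is missing from diarrhoea incidence, and a complication that follows it has no trigger. The same episode in the UK or Spain can enter both counts. The outcome therefore carries one name but two levels of ascertainment.

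What is at stake first is absolute incidence. A low Swedish figure, or a pooled figure that includes it, could be read as reassuring when it partly reflects where the data come from. The second issue is interpretation of the odds ratio (OR). A pooled OR would mix an outcome recorded in hospital or specialist care with one that includes primary-care events, with no country term to show it.

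**Working it through.** **1. The 9.9 justification against the rest of the protocol.** Section 9.9 says that specialist diagnoses are what the variables are expected to need. Section 4.6 says that all variables come from GP records, which cannot hold for Sweden. Section 9.3.2 uses primary-care laboratory results. Section 9.2.1.2 counts dizziness, vertigo and oral rehydration as SCD. Section 9.9 also says that comorbidities are identifiable only where a GP was consulted, which cannot describe Sweden either. These statements need reconciling.

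**2. The plan's own figures (Section 9.5).** Trial diarrhoea is 19.6% on linaclotide and 3% on placebo, of which 10.1% and 4% are severe.
- 0.196 × 0.101 = 1.98% (stated 1.99%)
- 0.03 × 0.04 = 0.12% (stated 0.13%)

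Both agree apart from rounding of the inputs. About 1 − 0.101 = 90% of linaclotide diarrhoea in those trials was not severe.

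**3. Effect of capture on Swedish incidence.** Let s be the share of episodes that the Swedish register records. The protocol gives no value, so s is an assumption. Observed incidence = 19.6% × s:

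| s | Observed |
|---|---|
| 100% | 19.6% |
| 50% | 9.8% |
| 25% | 4.9% |
| 10% | 2.0% |

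**4. Effect on a pooled incidence.** With Sweden at weight w and full capture elsewhere, observed/true = 1 − w(1 − s). Section 4.8 gives about 329,000 patients and Section 9.5.2 more than 200,000 in the UK. Sweden and Spain together are thus at most 129,000/329,000 = 39%, which is an upper bound for Sweden. At s = 10%, the pooled figure is 1 − 0.10 × 0.90 = 91% of the true one if w = 10%, and 1 − 0.39 × 0.90 = 65% if w = 39%. At s = 50% the two values are 95% and about 80%.

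**5. Effect on the OR.** Assume a true OR of 3 and SCD risk of 0.5% in non-users. Risk in users is then 3 × 0.005/(1 + 0.005 × 2) = 1.485%. Multiply each risk by its capture and recompute the OR:

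| Capture, non-users | Capture, users | Observed OR |
|---|---|---|
| 50% | 50% | 2.99 |
| 10% | 10% | 2.97 |
| 50% | 75% | 4.49 |
| 10% | 15% | 4.46 |
| 50% | 100% | 6.02 |
| 10% | 20% | 5.96 |

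Equal capture leaves the OR almost intact while up to 90% of events are lost. A comparison of country ORs would not show that loss. Capture 1.5 or 2 times as high in users moves the OR to about 4.5 or 6.0.

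**6. Study size.** The required pairs at 1% exposure among controls reproduce with the matched-pair formula. With P = OR/(1 + OR), discordant pairs m = [1.96/2 + 0.8416√(P(1 − P))]²/(P − 0.5)², divided by p0(1 − p1) + p1(1 − p0). For OR 3, 28.92/0.03882 = 744.9 (stated 745). For OR 4 the result is 400.8 (stated 401). Neither depends on Sweden.

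**The case against.** - **The gap is disclosed and country results come first.** True. Section 9.9 states the gap, 9.7 plans country-specific analyses, and pooling is conditional. But nothing says that the Swedish figure measures a different event, and neither the case definition nor the pooling rule takes the gap into account.
- **Swedish capture may be good.** The register includes outpatient visits since 2001, and its IBS-C patients already have specialist contact. GP records may also miss mild diarrhoea, so 19.6% need not be what the UK or Spain would show. This stands, and it is why the size is given only as a range.
- **A large gap would block pooling.** A reader might infer a pooled linaclotide incidence of about 11% (0.53 × 19.6% + 0.47 × 1.98% = 11.3%), with 10-fold and 25-fold under-counts. The documents do not support these as findings. They require that only severe diarrhoea is captured, and the 11% also needs a 47% Swedish share that was projected to December 2016 and has been overtaken by the UK extension. A gap that large would also probably fail a heterogeneity test on incidence: with 200 users a side (assumed), z = 0.176/0.0297 = 5.9. Smaller gaps, or a test on ORs only, have no such protection.
- **Section 4.6 is abstract shorthand.** Largely so: 4.7 and 9.3 describe the sources correctly. It remains inaccurate for Sweden.
- **Primary-care handling of milder components is an inference.** The protocol does not say where dizziness or oral rehydration is managed. It does, however, give no basis for saying that a specialist diagnosis is required for them.
- **Diarrhoea incidence may not be delivered.** Sections 9.5.1 and 9.7.1 make it conditional on predictive values; 4.9 and 8.2 do not. The point applies wherever it is reported.

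**Conclusion.** The point holds in a limited form. Swedish diarrhoea and SCD are hospital/specialist-recorded, the common definition does not say so, and the reassurance in 9.9 does not match the listed SCD components. Absolute incidence in Sweden is likely under-counted. The amount is unknown: across assumed capture of 10% to 100%, a true 19.6% would read between 2.0% and 19.6%.

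Three stronger readings should be resisted. First, the OR is not shown to be biased. That requires capture to differ by exposure, or the effect to differ in specialist-recorded patients, and the documents give no figure for either. Second, an admission that supplies both trigger and outcome is not peculiar to Sweden. It follows from listing hospitalisation due to diarrhoea in the common definition and can occur in UK and Spanish hospital data. Third, a ban on pooling ORs would be a preference and does not follow from the documents. No sample-size figure is wrong on this account.

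**What to change.** 1. In Sections 9.7 and 9.7.2.1, report crude incidence of diarrhoea and of SCD by country, and do not pool Sweden into either, whatever the heterogeneity test shows. A difference in what is recorded is not something that a test can settle.
2. In 9.2.1.2 and in all outputs, label Swedish outcomes *hospital/specialist-recorded*.
3. Report any three-country pooled OR alongside a UK-plus-Spain OR as a sensitivity analysis.
4. Optionally, add an SCD analysis restricted to hospital-recorded events in all three countries. In the UK this must be limited to HES-linked patients within HES coverage. Table 1 gives 31 March 2021 for HES APC, 31 October 2020 for HES OP and 31 March 2020 for HES AE, against October and November 2023 for the two CPRD datasets.
5. Replace the sentence in 9.9 with a statement of what is lost in Sweden and its likely direction, and correct the source statement in 4.6.

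**Cost.** Items 1, 2 and 5 are wording and table layout. Item 3 is one further model on data already planned. The UK-plus-Spain and hospital-only estimates will be less precise, and the hospital-only UK analysis loses follow-up and unlinked patients. The 745 pairs for an OR of 3 are 745/11,800 = 6.3% of the potential cases expected in Section 4.8. UK-plus-Spain power is therefore not obviously at risk, but the protocol does not split cases by country and validation will reduce them.

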4.8 STUDY SIZE

The sample size expected by 2016 in the three countries (available for analysis two to six months later) was at least 200,000 patients with IBS-C (cohort). Based on projected post-authorisation usage data provided by Almirall [MAH of linaclotide at the time of development of this protocol] in the linaclotide risk management plan (RMP), it was expected that roughly 9,665 patients using linaclotide could be captured by the proposed databases in the UK, Spain, and Sweden over the first four years of commercialisation, assuming Almirall [MAH of linaclotide at the time of development of this protocol] sales forecasts were correct, or approximately 5% of all patients with IBS-C would have been exposed to linaclotide.

In the progress report for 2016, users of linaclotide included in each of the study database were reported to be below the targeted numbers. Following the recommendation of the PRAC rapporteur, the end of the data collection was then extended by one year until December 2017. In October 2022, the PRAC recommended to further extend the study period in the UK until at least March 2021 or later if possible (the most recent CPRD and HES data at the time of data extraction), and include the CPRD Aurum dataset (in addition to the CPRD GOLD dataset originally proposed) to increase the sample size in the

UK.

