6 MILESTONES

Table 1. Milestones

Milestone	Date
Start of data collection	February 2013 (Sweden) May 2013 (UK) September 2014 (Spain)

End of data collection	Electronic datasets: 
- Spain and Sweden: Data collected up to December 2018. Effective date when data up to December 2018 can be accessed (incorporating time for data access applications to be processed)- UK: the most recent HES and CPRD data available at the time of data access in 2024, i.e., 20 October 2023 for CPRD Aurum, 17 November 2023 for CPRD GOLD 31 March 2021 for HES APC 31 October 2020
------------------------	--

Milestone	Date
	for HES OP, 31 March 2020 for HES AE and 29 March 2021 for ONS death data. Validation: - UK: Q2-Q3 2024 - Spain: Q2 2020 Analytical dataset completely available: Q4 2024
Registration in the EU PAS register	September 2016
Study progress reports	With each PSUR
Interim reports	No
Final report of study results	Q4 2024
EMA submission	Q1 2025

Abbreviations: CPRD Clinical Practice Research Datalink; EU European Union; GP general practitioner; HES Hospital Episode Statistics; PAS post authorisation study; PSUR periodic safety update report; UK United Kingdom; NPR National Patient Register; PDR Prescription Drug Register

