9.2.1.4 TIME PERIODS AND DATES

The study period is determined by the launch date of linaclotide, subsequent uptake, and length of time required to accrue a non-trivial number of SCD cases (see case definition above, Section 9.3 *Variables* and Section 9.5 *Study Size* below). The study period starts on the date of linaclotide commercialisation in each of the countries: in Sweden on February 2013, in the UK on May 2013, and in Spain on September 2014.

The end of data collection has been extended to November 2023 in the UK, and December 2018 in Sweden and in Spain, so the study period will include 50 months in Spain, approximately 10 years in the UK and 68 months in Sweden for medical and prescription data accrual, each database's lag time (for collected data to be available in each database, estimated in up to eight months or until August 2019), and seven months for initial data management and additional data collection from GPs (Q3 2019 for Spain and Sweden, and currently planned until Q3 2024 for the UK). Due to delays experienced in accessing data from the Swedish authorities, version 7.0. of the protocol proposed to extend the final delivery of the final report until June 2020. This is because data from Sweden was not anticipated to become available until Q3-Q4 2019. Version 9.0 of the protocol proposed to extend the final delivery of the final report to June 2022. A very low response rate by the UK GPs to questionnaires

sent to them in Q1 2020 to validate SCD diagnosis was observed. This was possibly because of the shut down in the UK due to COVID-19 infections. A decision was made to resend the questionnaire in Q1 2021. The continued COVID-19 related shutdown in the UK necessitated further postponement of resending the questionnaire to GPs. MAH proposed to resend the questionnaires in Q4 2021. When approached on this matter in Q4 2021, the planning manager at CPRD explained that CPRD paused all GP questionnaire studies until further notice due to the shortage of primary care clinical staff in the UK to continue focusing their resources on supporting COVID-19 activities. Version 11.0 of the protocol proposed to re-open UK validation study in October 2022 until January 2023 with planned study report in Q3 2023.

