In response to the MAH's proposal, in the preliminary assessment report for the PASS protocol amendment submission (3rd Oct 2022), PRAC requested the MAH to extend the UK observational period up to the most recent possible date in order to include all available data and to revise the data collection period in the milestones accordingly, without further postponement of the final report (Q3 2023). The MAH contacted CPRD to confirm next steps for data extraction and validation study rerun. CPRD required that the MAH submits a new protocol to the CPRD review committee before requesting the new datasets and re-running the validation study. This is due to the change of dataset from CPRD GOLD to CPRD GOLD and CPRD Aurum, and the change of the observational period. The MAH submitted a new protocol to CPRD in April 2023 and expected to receive approval and the new datasets in Q3 2023. However, the actual process from application submission to data access took almost 12 months and the final data cut was eventually delivered in March 2024. The identification of new potential SCD cases as well as the initiation of validation activities have been completed in Q2 2024.

The validation of the diagnosis and SCD cases ended in Q2 2020 in Spain and expected to end in Q3 2024 in the UK. There is no validation study in Sweden. This study period is expected to allow for sufficient follow-up (long-term safety assessment) for those enrolled during the first period after linaclotide launch and for any subpopulations of interest (those with increased risk of SCD) to have the opportunity to accrue a sizable number of subjects for descriptive purposes. Please refer to Section 9.5 *Study Size* and Section 9.7 *Data Analysis* below.

[figure not shown]
The IBS-C cohort entry date for each cohort member will be defined as the date IBS-C criteria are first fulfilled or 01 February 2013 in Sweden, 13 May 2013 in the UK, and 01 September 2014 in Spain (linaclotide launch dates), whichever is the latest.

The follow-up period for each study subject in the IBS-C cohort will be from the cohort entry date to the earliest of the following (end of follow-up date; one day is the minimum follow-up (Figure 1):

- End of the study period
- Disenrollment from the database (date of transfer out of the practice or the PCP or Sweden)
- Date of last data collection for the practice
- Death
- Index date

The baseline period is the ≥ 12 -month period before IBS-C cohort entry date.

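### UK follow-up runs to October/November 2023 with no end-of-linkage date, although all hospital linkage stops between March 2020 and March 2021, so UK SCD rates and the Cox model mix linked and unlinked time

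*Protocol*

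**What the plan says.** Section 9.2.1.4 sets the follow-up rule: "The follow-up period for each study subject in the IBS-C cohort will be from the cohort entry date" to the earliest of study end, disenrolment, last data collection for the practice, death or index date. The practice item concerns the practice's own data, not HES. UK entry begins on "13 May 2013 in the UK", and the same section states "The end of data collection has been extended to November 2023 in the UK".

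Table 1 in section 6 gives the UK end dates: "20 October 2023 for CPRD Aurum, 17 November 2023 for CPRD GOLD 31 March 2021 for HES APC 31 October 2020", continuing "for HES OP, 31 March 2020 for HES AE and 29 March 2021 for ONS death data".

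Section 9.7.2.1 uses person-time at risk as the denominator of the incidence rates. Section 9.7.2.2 adds a Cox model. For SCD, both run only if validation reaches a PPV of at least 95% and an NPV of at least 99%.

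Section 9.9 acknowledges that the HES sources have different coverage periods, singles out HES OP and HES AE as shorter than HES APC, and concludes "This might increase the risk of SCD cases being underestimated".

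Section 9.2.1.3 matches UK controls to cases on linkage availability at index date and gives each control the index date of its case.

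**The concern.** The case definition in section 9.2.1.2 includes components usually treated in hospital: admission for diarrhoea, intravenous rehydration, acute renal failure, hypovolaemic shock, coma. Once linkage ends, these can be found only as far as they reach GP records, the CPRD death flag or the validation questionnaire, while the patient's time still counts as time at risk.

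The crude SCD incidence in linaclotide users, overall and in the higher-risk groups, is a conditional objective (section 8.2). A rate built on mixed ascertainment would be too low. A hazard ratio could also shift if exposed and unexposed time fall differently across the linked and unlinked periods. In addition, section 9.7.2.1 plots rates over follow-up to decide whether to split it into intervals. A drop in ascertainment could be read there as a falling risk.

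Section 9.9 does not settle the matter. It compares the HES sources only with one another and never says that all of them stop well before the CPRD data. Its earlier reassurance, that missed endpoints should affect only milder complications, does not fit a gap in hospital records.

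**Working it through.** **Inputs.** UK start 13 May 2013 (section 9.2.1.4). CPRD, HES and ONS end dates from Table 1.

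**UK window.** 13 May 2013 to 20 October 2023 is 3,812 days = 10.44 years (Aurum). To 17 November 2023 it is 3,840 days = 10.51 years (GOLD). Both agree with the roughly 10 years stated in section 9.2.1.4.

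**Calendar share without linkage** = (CPRD end − linkage end) / window:

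| Source | Aurum | GOLD |
|---|---|---|
| HES APC | 933/3,812 = 24.5% | 961/3,840 = 25.0% |
| ONS deaths | 935/3,812 = 24.5% | 963/3,840 = 25.1% |
| HES OP | 1,084/3,812 = 28.4% | 1,112/3,840 = 29.0% |
| HES AE | 1,298/3,812 = 34.1% | 1,326/3,840 = 34.5% |

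The HES gaps run from 933 days (2.6 years) to 1,326 days (3.6 years).

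**Person-time share (assumptions needed).** The documents give no entry or exit rates. Assume a share p of the cohort is prevalent at launch, the rest enters uniformly, and patients leave at a constant rate x per year. The number at risk is then proportional to p·e^(−xt) + [(1−p)/T]·(1−e^(−xt))/x, with T = 10.44 years; for x = 0 it is p + (1−p)·t/T. Integrating after each linkage end:

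- p = 100%, x = 15%: APC 12%, AE 19%
- p = 50%, x = 8%: APC 25%, AE 35%
- p = 30%, x = 0: APC 34%, AE 46%

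**Understatement of the crude UK rate.** Let f be the unlinked person-time share and h the share of SCD seen only in HES. With a constant true rate, observed/true = 1 − h·f. The documents do not give h. With h assumed at 10% to 50% and the APC range for f:

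- low: 0.10 × 0.12 = 1.2%
- high: 0.50 × 0.34 = 17%

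**Hazard ratio.** Let f_e and f_u be the unlinked shares of exposed and unexposed time. Without calendar-time control the ratio is multiplied by about (1 − f_e·h)/(1 − f_u·h).

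- Exposed time later (f_e = 35% to 45%, f_u = 25%, h = 25% to 50%): from 0.9125/0.9375 = 0.97 to 0.775/0.875 = 0.89.
- The same values swapped, so exposed time earlier: from 0.9375/0.9125 = 1.03 to 0.875/0.775 = 1.13.
- f_e = f_u: factor 1, no bias.

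All these shares are assumptions. The calculation shows only that size and direction depend on a distribution the documents do not report.

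**The case against.** **The affected analyses are conditional.** Section 8.2 makes SCD incidence an objective only if validation allows it, and sections 9.7.1 and 9.7.2.2 otherwise leave only the nested case-control analysis. This stands and limits the point. The matched odds ratio is largely protected, because case and control share the index date and linkage status. The gap mainly costs cases, although an undetected case could be drawn as a control. The analyses remain planned, however, and their follow-up rule is already written.

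**Hospital SCD does not vanish.** A reader might infer that it cannot be seen at all after linkage ends. The documents do not support that. Section 4.6 identifies variables from GP records, Annex 3 takes UK death from a CPRD flag, and the questionnaire asks about admission, emergency care and intravenous rehydration. Dizziness, vertigo or mild potassium loss can plausibly be recorded in primary care. The substitute is still partial: the questionnaire covers cases and controls rather than the cohort, and Annex 3 notes that CPRD lacks detailed secondary-care information.

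**Bias towards no harm is not established.** It is tempting to argue that uptake was slow, so exposed time lies late. The documents give no calendar distribution of UK exposed time, and Annex 3 already counts 474 linaclotide patients in the December 2014 CPRD version.

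**The problem is disclosed, and the extension was requested.** Section 4.8 records that "the PRAC recommended to further extend the study period in the UK until at least March 2021 or later if possible", and section 9.2.1.4 reports a request for data to the most recent possible date. That is a good reason to keep the full-period analysis. It is no reason to leave it without a linkage-period comparison.

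**Conclusion.** The point holds for the UK cohort analyses of SCD, if they run. As written, they combine time with and without hospital ascertainment, and the disclosure in section 9.9 does not correct this.

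The firm figures are shares of the calendar window: about 25% without inpatient, 29% without outpatient and 35% without A&E linkage. They should not be read as shares of person-time, and the third applies to A&E data only.

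For any h above zero the crude UK rate is understated. The 1% to 17% range rests on assumed h, entry and exit rates, and on a constant true rate. The Cox hazard ratio may be biased either way or not at all. The nested case-control odds ratio is not materially called into question. This is a change that should be made, not one that threatens the study.

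**What to change.** 1. For the UK SCD incidence rates and the Cox model, add an analysis in linkage-eligible patients that ends follow-up at the end of HES APC coverage, 31 March 2021. Report it beside the full-period analysis, which answers the PRAC request for all available data.

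2. Stratify or adjust the full-period analysis by linkage period: to 31 March 2020 (all HES sources); to 31 October 2020 (APC and OP); to 31 March 2021 (APC only); thereafter none. The same periods matter inside the censored analysis, because HES AE and HES OP end 12 and 5 months before HES APC. Stratification makes the hazard ratio comparable within periods if under-ascertainment is similar in users and non-users. It does not restore the absolute rate after linkage ends.

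3. Amend section 9.9 to state that all HES sources stop about 2.6 to 3.6 years before the CPRD data and that hospital-treated SCD may be missed as a result.

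No new data are needed. The censored window is 3,840 − 961 = 2,879 days, about 7.9 years instead of 10.4 to 10.5. With fewer UK person-years and linaclotide users, its intervals will be wider. Annex 3 says linkage is only partial and section 4.8 that user numbers were below target, so this loss is real and cannot be sized from the documents. That is why the two analyses should stand side by side.
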